Visit 7 (Day 9 +/- 7): Subjects will be asked to return to the clinic for Visit 7 for follow-up. Subjects will be asked to refrain from bathing, exercising, or showering starting at 12:01am of Visit 7. Vital signs will be taken. Any adverse events since the last visit will be recorded. A brief exam of the skin on subjects' arms will be performed. For subjects with AD, the severity of AD on each arm will be graded using the localized SCORAD, modified EASI, and global SCORAD and EASI grading. Subjects will also be asked to grade their pruritus on a scale of 1-10, with 10 being the worst pruritus of their life. Digital photographs of the lesional skin on both arms will be taken. Next, one culture swab and one to two DNA swabs will be taken from the eczematous skin from each arm, and one culture swab and one to two DNA swabs will be taken from the non-lesional skin on the upper inner arm for a total of up to twelve (12) swabs. We expect this visit to take approximately 15 minutes.

Visit 8 (Day 11 +/- 7): Subjects will be asked to return to the clinic for Visit 8 for follow-up. Subjects will be asked to refrain from bathing, exercising, or showering starting at 12:01am of Visit 8. Vital signs will be taken. Any adverse events since the last visit will be recorded. A brief exam of the skin on subjects' arms will be performed. For subjects with AD, the severity of AD on each arm will be graded using the modified EASI, and global SCORAD and EASI grading. Subjects will also be asked to grade their pruritus on a scale of 1-10, with 10 being the worst pruritus of their life. Digital photographs of the lesional skin on both arms will be taken. Next, one culture swab and one to two DNA swabs will be taken from the eczematous skin from each arm, and one culture swab and one to two DNA swabs will be taken from the non-lesional skin on the upper inner arm for a total of up to twelve (12) swabs. At the conclusion of this visit, subjects may resume prohibited medications, as needed, and may use their choice of soap and emollient. We expect this visit to take approximately 15 minutes.

Visit 9, Phone 2 (Day 38 +/- 7 days)

Subjects will be called approximately one month after their Visit 6. During this phone call, subjects will be asked about any adverse events (including serious adverse events) since their last follow-up visit, as well as how their eczema is currently doing. Although this phone contact will be the last scheduled contact for subjects with respect to this study, any subject with an ongoing adverse event (including serious adverse event) at the time of this phone contact will continue to be followed by study personnel until resolution of the event.

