6.2. Study Design – dose schedule

The dosing schedule for the AMT cream or the Vehicle (Cetaphil® lotion) is described in Sections 8.3 and 8.5.

The first dose of the AMT cream or Vehicle cream will be administered to the subjects at the clinical site on Day 0 (Treatment Initiation Visit). At that time, they will be guided and given a handout instructing them to apply the AMT or Vehicle cream uniformly across both arms (this area will include *S. aureus* colonized lesions as well as non-lesional skin) twice daily for seven days. The participants will also be provided a subject diary and 18 single-use containers for dosing at home. An additional 14 single-use packets of AMT Product or Vehicle Product will be dispensed at the next clinic visit on Day 4 to use until Day 7. Subjects will be instructed that 2 additional single-use containers will be provided to them at Day 0 and Day 4 in the event that the subject should misplace a container of study cream. Accountability of the study creams will be performed, and subjects will be asked to return the jars of used and unused cream at the next in-clinic visit.

At the clinic visits on Day 4 and Day 7, the subjects will provide skin swab samples and be assessed for adverse events (AEs). Three additional clinic visits will be scheduled to assess safety and stability of the AMT cream. There will be a 30 day follow-up of all participants after the last treatment to assess safety and disease status. This will be brief phone call, and subjects will be asked to report any new adverse events and to answer questions regarding the status of their AD. Any subject with an ongoing AE/SAE at the time of this phone contact will continue to be followed until the event is resolved with or without sequelae.

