identified when uploaded. Next, up to 3 skin swabs will be performed on each arm in a region of eczematous skin and non-lesional skin, for a total of up to 12 swabs. For the skin swabs, one culture swab and one to two DNA swabs will be taken from the eczematous skin from each arm, and one culture swab and one to two DNA swabs will be taken from the non-lesional skin on each upper inner arm for a total of up to twelve (12) swabs. After swabbing, the swabs are placed into either an empty Eppendorf tube (if analyzing the DNA of the bacteria present on the skin surface) or into a liquid medium such as tryptic soy broth (if analyzing the amount of bacteria present on the swabbed skin surface). These swabs will be analyzed in the lab to determine how many and what type of bacteria are present. The AMT cream or vehicle cream will then be applied to both arms by the gloved hands of a study coordinator. The moisturizers will be provided by [name] laboratory and will be in identical containers labeled either A or B. Neither the study coordinator nor the subject will know which cream is in which container. Container A or B will contain either Cetaphil alone or Cetaphil plus colonies of the subject's endogenous AMP-producing Staph grown in the lab from the subject's screening swab. A thin coat of cream A or B will be applied to both arms (excluding hand) in order to demonstrate proper application. Up to twelve (12) skin swabs will then be performed on both arms in the areas of cream application on lesional and non-lesional skin, between 5 minutes to an hour after cream application, depending on the discretion of the investigator. Following the skin swabs, the Cetaphil alone or Cetaphil with AMP-producing Staph will be reapplied onto the subjects' arms as previously described. The subject will be instructed to withhold use of any topical or oral AD medications until after their last in-clinic follow-up visit (Visit 8). The subject will be provided with aliquots of either the transplant or vehicle creams, enough for at least 4 days of application. Subjects will be instructed to apply the cream twice a day for the next 4 days, and will be instructed to apply the provided cream from one aliquot per arm. To minimize cross contamination, we will instruct subjects to wear long sleeve clothes and change into clean clothes every day. All creams should be stored at room temperature. Subjects will be reminded to use Dove soap provided to them, whenever they shower, but to avoid the upper extremities, until after their last in-clinic visit on Day 11 is complete. Subjects will be instructed to continue their daily skin care routine, and discouraged from using antibacterial soaps and swimming in the ocean or pool until their last in-clinic follow-up visit. They will also be instructed that if these events occur, to please notify the study staff at their next visit. At the end of the visit, subjects will be given an instruction sheet and a subject diary to assess for cream application appliance. They will be asked to bring the diary pages to their Follow-up Visit 4. This will conclude the treatment visit. We expect this visit to take approximately 20 minutes.

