
Optional Visit 1 (1 hour after cream application +/- 2 hours): Subjects will have the option to return to clinic for an optional visit approximately 1 hour after AMT cream application. At this optional visit, up to 12 skin swabs will be taken of the lesional and non-lesional skin on the arms (one culture swab and one to two DNA swabs for lesional and non-lesional skin of each arm). This visit will take approximately 15 minutes.

Optional Visit 2 (4 hours after cream application +/- 2 hours): Subjects will have the option to return to clinic for an optional visit approximately 4 hours after AMT cream application. At this optional visit, up to 12 skin swabs will be taken of the lesional arms and non-lesional skin on the arms (one culture swab and one to two DNA swabs for lesional and non-lesional skin of each arm). This visit will take approximately 15 minutes.

Visit 4 (Day 4 +/- 5): Subjects will return to the clinic to pick up fresh aliquots of the AMT or vehicle creams, and to return approximately 4 hours after last cream application. Any adverse events will be recorded. Subjects will be asked to refrain from bathing, exercising, or showering starting at 12:01am of Visit 4. Vital signs will be taken. Subject diaries will be collected at this time and a new subject diary will be dispensed to assess for cream application appliance. Used aliquots of cream will be collected at this visit. The localized SCORAD, modified EASI, global EASI and SCORAD grading scale will be used to rate the severity of the lesional AD skin on the subject's bilateral arms, and the extent of lesional AD skin on each arm will be recorded. Digital photographs of the lesional skin on both arms will be taken. Each photograph will also include a ruler so the scale of the lesions can be determined, as well as a card with the subject's identification number, visit date, and photograph location so that the photographs can be identified when uploaded. Next, one culture swab and one to two DNA swabs will be taken from the eczematous skin from each arm, and one culture swab and one to two DNA swabs will be taken from the non-lesional skin on each upper inner arm for a total of up to twelve (12) swabs. We expect this visit to take approximately 15 minutes.

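### The Visit 4 resupply window (Day 4 +/- 5 days) does not fit the cream dispensed on Day 0: a visit on Day 7 to 9 means 3 to 6 of 14 applications missed, or about 2 to 5 days without cream if the course is extended

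*Combined protocol and SAP*

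**What the plan says.** Visit 4 is the resupply visit. Section 8.3 reads "Visit 4 (Day 4 +/- 5): Subjects will return to the clinic to pick up fresh aliquots of the AMT or vehicle creams", and the Schedule of Events (Table 1, section 8.5) gives the same window. The visit is also meant to be timed to dosing: subjects are to "return approximately 4 hours after last cream application".

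Section 6.2 sets the supply. On Day 0: "The participants will also be provided a subject diary and 18 single-use containers for dosing at home". Then: "An additional 14 single-use packets of AMT Product or Vehicle Product will be dispensed at the next clinic visit on Day 4", to last until Day 7. On spares: "Subjects will be instructed that 2 additional single-use containers will be provided to them at Day 0 and Day 4". On the clinic dose: "The first dose of the AMT cream or Vehicle cream will be administered to the subjects at the clinical site on Day 0". Under Visit 3 in section 8.3, subjects "will be instructed to apply the provided cream from one aliquot per arm", and the Day 0 supply is described as "enough for at least 4 days of application".

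The course is twice daily on both arms for seven days (sections 3.1 and 6.2). Sections 6.2 and 6.4 and Table 1 have unused cream returned.

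**The concern.** The window opens the day before the first dose and closes two days after the planned end of treatment, while the Day 0 supply lasts only until Day 4 or early Day 5. A visit can therefore fall inside the window when the subject has had no cream for days. Such a visit cannot meet the 4-hour timing instruction. The plan has no bridging supply, and no rule on whether a subject resupplied late stops at Day 7 or makes up the missed applications, so two coordinators could handle identical cases differently.

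The primary endpoint is the change in *S. aureus* after 7 days of cream. Section 1.4 justifies repeated dosing by the loss of most transplanted bacteria within 24 hours of a single application, so an interruption of several days works against the reason for the regimen. Late attendance is foreseeable. Section 12.2 treats visit dates as flexible and has a visit rescheduled to preserve a 7-day washout if a subject needs topical treatment for a severe flare. Topical use on Day 1 or 2 would put Visit 4 on Day 8 or 9. Part of that section seems to be written for a single-application design, but it is current text.

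**Working it through.** **Inputs.** Visit 4 window: 4 - 5 = Day -1 to 4 + 5 = Day 9 (section 8.3, Table 1). Containers: 18 on Day 0 and 14 at Visit 4, with 2 spares at each dispensing (6.2). Use: one container per arm, so 2 per application and 4 per day (8.3). Course: 7 x 2 = 14 applications.

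**The plan's own counts.** Day 0: 4 days x 4 + 2 spares = 18. Visit 4: 3 days x 4 + 2 spares = 14. Both reproduce exactly, which also shows that the spares are included in the 18 and 14. Without spares, (16 + 12) / 2 = 14 applications. The supply is sized correctly for a visit on Day 4.

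**When the Day 0 supply runs out.** Home applications: 18 / 2 = 9 with the spares used, 16 / 2 = 8 without.
- Clinic dose in the morning, first home dose Day 0 PM: the last is Day 4 PM (9) or Day 4 AM (8).
- Clinic dose in the afternoon, first home dose Day 1 AM: the last is Day 5 AM (9) or Day 4 PM (8).

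**Applications missed if the course is not extended.** This counts the half-day slots of the 14-application schedule for which the subject has no cream. The range covers 2 x 2 x 2 x 2 = 16 cases: clinic dose morning or afternoon, counted towards the 14 or not, spares used or not, visit before or after that day's morning dose. The last two columns assume a morning clinic dose, spares used, and the visit after the morning slot.

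| Visit 4 on | Range, 16 cases | Clinic dose counted | Clinic dose not counted |
|---|---|---|---|
| Day 5 | 0 to 2 | 1 | 1 |
| Day 6 | 1 to 4 | 3 | 3 |
| Day 7 | 3 to 6 | 4 | 5 |
| Days 8, 9 | 4 to 6 | 4 | 5 |

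On Days 1 to 4 the count is 0 if unused cream is kept. Worked cases:
- Counted: 14 - 9 - 1 = 4. Not counted: 14 - 9 = 5.
- Minimum of 3: afternoon clinic dose, spares used, resupply before the Day 7 morning dose. Day 5 PM, Day 6 AM and Day 6 PM are missed.
- Maximum of 6: not counted, spares unused, 14 - 8 = 6.

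As shares of the course, 3/14 = 21% and 6/14 = 43%.

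**Time without cream if the course is extended.** Shortest: last dose Day 5 AM, visit Day 7 AM, 2 days. With a morning clinic dose and spares used: Day 4 PM to midday on Day 9, about 4.5 days. Longest, spares unused: Day 4 AM to midday on Day 9, about 5 days. The supply would allow an extension, since (18 + 14) / 2 = 16 applications. With the clinic dose not counted, a Day 9 resupply leaves 14 - 9 = 5 applications, Day 9 PM to Day 11 PM.

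**Early visit.** Unused cream is returned, so a visit on Day 3 can also leave the subject short. With a morning clinic dose not counted, 6 home applications have been used and 8 remain, but 14 containers cover 7, which is 1 short (0 to 4 over the cases).

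**The case against.** The strongest reply is that the operating target is clear. Section 3.1 puts the visit 4 days after treatment, section 6.2 says Day 4, and the Visit 3 text gives 4 days of home dosing. Only the late tail causes harm, and the Day -1 edge is nominal because nobody is resupplied before being supplied. This stands as a limit on the size of the problem, but it does not make the window fit.

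A reader might infer that the container counts are wrong. They are not: both reproduce exactly.

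A reader might also infer that a subject resupplied late is fully compliant. The documents do not support that. Missing applications departs from twice daily for seven days, section 15.1 makes any departure from procedures a deviation, and the per-protocol set in section 13.4.1 can exclude the subject. Keeping the subject in the intention-to-treat analysis is what that analysis is for. These rules, with the diaries and weighed returns, record the gap afterwards but do not prevent it.

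Nor is there a single figure for doses missed. The value of 5 leaves out the clinic dose, although section 6.2 calls it the first dose; counting it gives 4.

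Finally, section 1.3 reports 50% viability at day 5, from which a reader might infer that Day 0 cream should not be used that late. Section 6.1.1.1 allows room-temperature storage for up to a week, so the documents do not rule it out.

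**Conclusion.** The concern holds as a mismatch between the visit window and the supply. A Visit 4 held on Day 7 to 9, inside the stated window, means 3 to 6 of 14 applications missed (about 4 if the clinic dose counts, about 5 if it does not, with a morning clinic dose and spares used), or about 2 to 5 days without cream if the course is extended.

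This assumes half-day dosing slots, a first home dose on Day 0 PM or Day 1 AM, no lost containers, and spares included in the 18. If the spares came on top (20 containers, 10 home applications), 14 - 10 = 4 or 14 - 10 - 1 = 3 would be missed, with 2 as an extreme.

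The documents do not say how many subjects would attend late, so no effect on the primary comparison can be given. Each such subject in the AMT arm is 1 of 18 (5.6%). The change is worth making because it is cheap and protects the exposure that the primary endpoint presupposes.

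**What to change.** 1. In section 8.3 and Table 1, narrow the Visit 4 window to about Day 4 +/- 1 day.
2. In section 6.2, state that the Day 0 clinic dose is application 1 of 14, and whether applications missed before a late resupply are made up or the course ends as scheduled.
3. Dispense 22 containers on Day 0 (5 x 4 + 2) and 18 at Visit 4 (4 x 4 + 2).

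Check, with the clinic dose counted (13 home applications), unused cream returned, and the visit after the morning dose:
- Day 5 visit: at most 10 home applications are needed beforehand (Day 0 PM to Day 5 AM), and 20 / 2 = 10 without spares.
- Day 3 visit: at most 13 - 5 = 8 remain, and 16 / 2 = 8 without spares.

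Nothing is missed. If the clinic dose were not counted and were given in the afternoon, a Day 3 visit would leave 9 applications, which uses the 2 spares.

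Cost: protocol wording, tighter scheduling of one visit, and up to (22 - 18) + (18 - 14) = 8 more containers per subject. No added patients.

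This does not settle the Visit 5 window (Day 7 +/- 7 days), within which the primary endpoint is read. That is a separate issue.

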3.1. Description of Study Design

This is a single site, double blind placebo controlled study, which will assess the efficacy, safety, and steady state of Autologous Microbiome Transplant (AMT) cream in adults with AD. After providing informed consent, patients will be assessed for study eligibility at the screening visit, in which participants will consent to all of the study experiments separately. Subjects that withdraw from the study will be replaced. Eligible subjects will be randomized to receive either AMT cream or placebo in a 2:1 allocation ratio (AMT cream: placebo).

Subjects will be instructed to apply either the AMT or vehicle cream to both arms twice a day for seven days. Both subjects and clinical investigators will be blinded. Optional follow-up visits to assess clinical effect and steady state may occur at 1 and 4 hours after initial cream application if the subjects are willing to return at these time points. 4 days after the treatment visit, subjects will return to the clinic for fresh aliquots of the AMT and vehicle creams as well as to assess safety and clinical effect. Subjects will return to clinic after the seven day course of AMT or vehicle creams for clinical and safety assessments. Subjects will then be asked to return to the clinic 1 day after completion of the AMT or vehicle cream course for additional safety and clinical effect assessments. Subsequently, subjects will return for additional follow-up visits only if their lesional atopic dermatitis sites have not yet returned to baseline (*S. aureus* is no longer inhibited and *Staph species* from the AMT cream is zero). Up to 27 subjects will be recruited for this entire study. The duration of this study is approximately 2 months. We anticipate the entire study duration will be approximately 2 years total, and that it will take approximately 1 year to reach recruitment and enrollment goals for this study. The study flow diagram is provided in Figure 1.

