Visit 5 (Day 7 +/- 7): Subjects will be asked to return to the clinic for Visit 5 approximately 4 hours after last cream application. Subject diaries will be collected at this time. Any used and unused aliquots of cream will be collected at this visit. Subjects will be asked to refrain from bathing, exercising, or showering starting at 12:01am of Visit 5. Vital signs will be taken. Any adverse events since the last visit will be recorded. A brief exam of the skin on subjects' arms will be performed. The severity of AD on each arm will be graded using the localized SCORAD, modified EASI and global SCORAD and EASI grading. Subjects will also be asked to grade their pruritus on a scale of 1-10, with 10 being the worst pruritus of their life. Digital photographs of the lesional skin on both arms will be taken. Next, one culture swab and one to two DNA swabs will be taken from the eczematous skin from each arm, and one culture swab and one to two DNA swabs will be taken from the non-lesional skin on each upper inner arm for a total of up to twelve (12) swabs to determine the microbial diversity and abundance. We expect this visit to take approximately 15 minutes.

Visit 6 (Day 8 +/- 7): Subjects will be asked to return to the clinic for follow-up. Any adverse events since the last visit will be recorded. A brief exam of the skin on subjects' arms will be performed. Subjects will be asked to refrain from bathing, exercising, or showering starting at 12:01am of Visit 6. Vital signs will be taken. The severity of AD on each arm will be graded using the localized SCORAD, modified EASI, and global SCORAD and EASI grading. Subjects will also be asked to grade their pruritus on a scale of 1-10, with 10 being the worst pruritus of their life. Digital photographs of the lesional skin on both arms will be taken. Next, one culture swab and one to two DNA swabs will be taken from the eczematous skin from each arm, and one culture swab and one to two DNA swabs will be taken from the non-lesional skin on each upper inner arm for a total of up to twelve (12) swabs. Any used cream will be collected. We expect this visit to take approximately 15 minutes.

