If the subject calls to report a possible infection during a time when the clinic is closed, the subject will be directed to the resident on call or closest urgent care facility for further management.

2. Risk of medication withdrawal: Discontinuation of a person's AD medication prior to participating in this study and also the prohibition of using AD medications for periods of time during this study may result in worsening or temporary flaring of the patient's AD.

As listed in the inclusion/exclusion criteria (section 10), subjects with severe AD who may have difficulty tolerating periods without medication use will be excluded from participating. Subjects enrolled in the study will be able to use over-the-counter moisturizers as needed. Moisturizers play a role in helping to prevent and control AD flares, and therefore may be of use to subjects whose AD is worsening. The time during which subjects are unable to treat their AD during the study will be limited to the 7-days prior to each screening and treatment/follow-up visit for topical medications, and 28-days prior to each screening and treatment/follow-up visit for oral medications. If for some reason severe worsening of AD occurs during a time in the study that subjects are not permitted to use their medication, the subject will be permitted to use their medication, however the upcoming visit must be rescheduled so that the required 7-day and 28-day wash-out periods before each screening and treatment/follow-up visits are observed. Since the visit dates for the study are relatively flexible (the only real time-dependent visit is the Follow-up Visit, which must occur approximately 24 hours after the Treatment Visit), rescheduling subject visits should not affect study results. AD itself is a chronic condition characterized by periods of flaring and remission. Any worsening of the subject's AD would constitute a disease flare that should be correctable with the use of medications. Flares of AD do not result in permanent deterioration of the subject's

condition. Finally, topical medication discontinuation must only be observed on the subject's bilateral arms since this is the site being studied during the trial. Subjects may treat the AD on all other body surfaces with topical medications throughout the study.

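### The +/-7 day windows for Visits 5 to 8 are too loose for the plan's own post-treatment time points, and the analyses after stopping do not repair this

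*Combined protocol and SAP*

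**What the plan says.** **Windows.** Section 8.3 schedules Visit 5 as "Day 7 +/- 7): Subjects will be asked to return to the clinic for Visit 5 approximately 4 hours after last cream application". The next visits follow the same pattern: "Visit 6 (Day 8 +/- 7): Subjects will be asked to return to the clinic for follow-up", Visit 7 at Day 9 +/- 7, and "Visit 8 (Day 11 +/- 7): Subjects will be asked to return to the clinic for Visit 8 for follow-up". Table 1 in section 8.5 repeats these windows, and its legend separates days from hours, so the 7 is not a misprint for hours.

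**Timing anchors.** Section 3.1 says of Visit 5: "Subjects will return to clinic after the seven day course of AMT or vehicle creams for clinical and safety assessments". Of Visit 6 it says: "Subjects will then be asked to return to the clinic 1 day after completion of the AMT or vehicle cream course". The synopsis and section 13.2.2 define persistence of the transplanted strains, and the change in S. aureus after stopping, at 1, 2 and 4 days.

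**Attendance.** Section 3.1 adds that after Visit 6 "subjects will return for additional follow-up visits only if their lesional atopic dermatitis sites have not yet returned to baseline", where baseline is judged by S. aureus inhibition and the transplanted strains. Section 8.3 and Table 1 schedule Visits 7 and 8 without that condition.

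**Analysis.** In 13.4.4, the CoNS persistence analyses (lesional item 2a, non-lesional item 3a) apply a t-test between arms at each nominal day. Both items give the last day first as 39 and then as 38. The S. aureus items meant for the period after stopping (lesional 3a, non-lesional 4a) list baseline, 1 hour, 4 hours, Day 4 and Day 7.

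**Flexibility.** Section 12.2 states that "rescheduling subject visits should not affect study results". It names as the only time-dependent visit one about 24 hours after the Treatment Visit, which this schedule does not contain.

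**The concern.** Time since last application is the quantity that the persistence endpoints study. Section 1.4 reports that most transplanted CoNS died within 24 hours of a single application, and gives this as the reason for repeated dosing. If a swab labelled 1 day may in fact be taken several days after stopping, a low count could mean poor persistence or a late swab, and the written analysis cannot tell the two apart. With 18 and 9 subjects, a few mistimed swabs carry weight.

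The Visit 5 window also touches the primary endpoint, because its wording allows the end-of-treatment swab before the course is finished. Separately, the 1-, 2- and 4-day S. aureus endpoints have no matching analysis at all.

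**Working it through.** **1. The nominal schedule reproduces the endpoints.** Take Day 7 as end of treatment: 8 - 7 = 1, 9 - 7 = 2, 11 - 7 = 4 days. Section 13 calls baseline day 28, so subtracting 28 from Days 35, 36, 37 and 39 gives Days 7, 8, 9 and 11. Visits on their nominal days meet both window and anchor.

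**2. The windows as written (centre +/- 7 days).**

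| Visit | Permitted days | Anchor |
|---|---|---|
| 5 | 0 to 14 | after the course, about 4 hours after last application |
| 6 | 1 to 15 | 1 day after |
| 7 | 2 to 16 | 2 days after |
| 8 | 4 to 18 | 4 days after |

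**3. Permitted time since last application.** Assume Visit 5 and the last application are on Day 7, and Visits 5 < 6 < 7 < 8 fall on separate days.
- Visit 6: Days 8 to 15, or 1 to 8 days after.
- Visit 7: Days 9 to 16, or 2 to 9 days after.
- Visit 8: Days 10 to 18, or 3 to 11 days after.

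If Visit 7 is b days after stopping, there are (b - 1) choices for Visit 6 and (11 - b) for Visit 8. Summing over b = 2 to 9: 9 + 16 + 21 + 24 + 25 + 24 + 21 + 16 = 156 ordered schedules. The overlap of 1-8, 2-9 and 3-11 is 3-8 days.

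**4. Visit 5 before the course ends.** Visit 3 is Day 0. With Visits 3, 4 and 5 on separate days, Visit 5 can be no earlier than Day 2. Days 2 to 14 are 13 days, of which Days 2 to 6 (5 days) precede completion of the course. Section 3.1 does not intend this.

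**5. The last persistence day.** Four days after Day 35 is Day 39. Day 38 is 38 - 35 = 3 days after stopping and corresponds to Day 10, which matches no nominal visit.

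**6. S. aureus after stopping.** The endpoint needs Days 36, 37 and 39, or Days 8, 9 and 11. The written analysis stops at Day 7, so none of the three is analysed.

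**7. Related supply check.** Visit 4 is Day 4 +/- 5, so Days -1 to 9. Section 6.2 dispenses 18 containers on Day 0; taking 2 of these as spares, and one container per arm twice a day (8.3), the supply covers (18 - 2)/4 = 4.0 days plus the spares. A resupply visit late in its window does not fit that supply.

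**The case against.** The strongest reply is that window and anchor should be read together, so that a visit must satisfy both. On that reading a Visit 6 several days late already departs from section 3.1, and the ranges above describe the windows alone. This stands, which is why the point is that the windows are too loose for the anchors and not that every in-window visit contradicts the plan. It does not supply a rule for analysing a late swab. The deviation definitions in 15.1 are broad enough to cover mistimed swabs, but neither they nor 13.4.1 say whether an in-window swab far from its anchor is a major violation. Visit dates and diaries may allow elapsed time to be recovered; nothing in section 13 says to use it.

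Stronger readings that a reader might infer, and that the documents do not support:
- *Nearly half of the Visit 5 window (Days 0 to 6, 7 of 15 days) precedes the end of the course.* Visits 3 and 4 must come first, which leaves 5 of 13 on separate days.
- *The spread in days implies an enormous fold difference in surviving CoNS.* The documents give no loss rate. Section 1.4 also reports CoNS near baseline at 24 hours after a single application, and the variable tested is the percentage of antimicrobial species, not absolute excess.
- *Randomisation and blinding leave only noise.* Under section 3.1, attendance at Visits 7 and 8 depends on S. aureus and transplanted-strain results, so it could differ by arm.
- *The arms will be biased.* That is not shown either.

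The hour-scale precedent, "Optional Visit 2 (4 hours after cream application +/- 2 hours", is limited. The 1-hour optional visit also has +/- 2 hours, so its window starts before application and overlaps the 4-hour one.

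**Conclusion.** The concern holds in this form. The windows in 8.3 and Table 1 do not protect the 4-hour, 1-, 2- and 4-day anchors, and the CoNS persistence analyses work by nominal day with no use of actual time. Offsets of 3 to 8 days after last application are acceptable under all three post-treatment labels, given Visit 5 and last application on Day 7 and visits in order. How often such visits would occur cannot be computed from the documents.

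Two parts need no assumption about visit behaviour. The S. aureus analyses after stopping omit every post-stopping day that the endpoint names. The last persistence day is given inconsistently, and the endpoint definition points to Day 39.

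The affected analyses are mainly secondary. For the primary endpoint, the window wording permits an early Visit 5, but section 3.1 does not intend it; a reader should not conclude that the primary result is compromised. The likely harm is blurred time points, with bias between arms not excluded because of the conditional attendance. This should be fixed.

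**What to change.** 1. **Section 13.4.** Record date and time of last application, and analyse Visit 5 to 8 swabs by actual time since then. Use either prespecified non-overlapping analysis windows, stating which swab is used when two fall in one window, or elapsed time in the model. Keep all swabs in the intention-to-treat analysis; apply any timing exclusion only in the per-protocol analysis.
2. **Section 8.3 and Table 1.** Replace +/-7 days with windows anchored to last application that do not overlap, each less than half the gap to the adjacent visit. With anchors at 4, 24, 48 and 96 hours the gaps are 20, 24 and 48 hours, so the half-gaps are 10, 12 and 24 hours. The exact hours are for the sponsor to choose.
3. **Section 13.4.4, lesional item 3a and non-lesional item 4a.** Analyse the 1-, 2- and 4-day swabs after stopping named in 13.2.2.
4. **Section 13.4.4, lesional item 2a and non-lesional item 3a.** Use Day 39 throughout.
5. **Reconcile** the visit-flexibility text in 12.2 with 3.1, 8.3, Table 1 and 13.2.2; the Visit 4 window with the supply in 6.2 and 8.3; and the conditional attendance at Visits 7 and 8 in 3.1 with the visits scheduled in 8.3 and Table 1.

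The cost is protocol wording, one recorded field and one analysis rule. The downside is tighter scheduling and some per-protocol exclusions, which matter with 18 and 9 subjects.
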